Study Center: UC Davis Comprehensive Cancer Center		
Planned Number of Subjects: 2-4 healthy subjects 2-4 NSCLC subjects		Study Development Phase: Phase I/II
Study Outcome Measures: 
 Quantitative assessment of [¹⁸F]F-AraG biodistribution in healthy tissues as a function of time. Quantitative assessment of [¹⁸F]F-AraG biodistribution in tumor lesions relative to non-malignant tissues in NSCLC subjects as a function of time. Recommended post-infusion time window to acquire a static [¹⁸F]F-AraG PET/CT scan. Quantitative assessment of change in PET signal pre- and post- first dose of PD-1/PD-L1 immunotherapy. 		

Study Flow Diagram (Healthy Subjects)

Study Flow Diagram (NSCLC Subjects)

NOTES:

1. IMMUNOTHERAPY IS NOT A PART OF THIS STUDY BUT IS A PART OF SOC TREATMENT OF THESE PATIENTS

IND	Investigational New Drug
IEC	Independent Ethics Committee
IP	Investigational Product
IRB	Institutional Review Board
ITT	Intent-to-Treat
IUD	Intra Uterine Device
IV	Intravenous
Kg	Kilograms
Mg	Milligram
mCi	MilliCurie
MRI	Magnetic resonance imaging
MedDRA	Medical Dictionary for Regulatory Activities
mg/dL	Milligram/deciliter
mmol/L	Millimole/Liter

msec	Milliseconds
NSCLC	Non-Small Cell Lung Cancer
PBMC	Peripheral Blood Monocyte Cells
PD1	Programmed cell death protein
PDL1	Programmed cell death protein ligand
PET	Positron emission tomography
PI	Principal Investigator
PK	Pharmacokinetics
PP	Per Protocol
RBC	Red Blood Cells
RECIST	Response evaluation criteria in solid tumors
RR	Respiration Rate
SAE	Serious Adverse Event
SAP	Statistical Analysis Plan
SD	Standard Deviation
SOC	Standard of Care
SOP	Standard Operating Procedures
SUV	Standardized uptake value
TBD	To be determined
TEAE	Treatment Emergent Adverse Event
TV	Treatment Visit
Tx	Treatment, Cancer Treatment
U/L	Units/Liter
USA	United States of America
USP	United States Pharmacopeia
WBC	White Blood Cells
WBS	Whole Body Scan
WHO	World Health Organization
µL	Microliter

1. BACKGROUND

1.1 Therapy Approaches for NSCLC

Lung cancer is the leading cause of cancer-related deaths in both men and women in the US. (<https://seer.cancer.gov/statfacts/html/lungb.html>). The majority of NSCLC patients present with advanced or metastatic disease, which is not amenable to surgical resection.

Immunotherapy has attracted much attention in recent years, since (i) identification of molecularly-defined tumor antigens (TA) [1, 20] has provided well defined moieties to be used as immunogens and as markers to monitor the immune response; (ii) characterization of the molecular steps leading to an immune response [5, 6] has facilitated the development of effective immunization strategies; and (iii) availability of cytokines has provided reagents to modulate the immune response. Because of the general belief that T cells play a major role in the control of tumor growth [15, 16], the application of T cell-based immunotherapy has been emphasized.

1.2 Immune-Checkpoint Blockade Immunotherapy Approaches

Immunotherapies have changed the treatment strategy of some types of tumor including melanoma and, more recently, non-small-cell lung cancer (NSCLC). Immune checkpoints are crucial for the maintenance of self-tolerance and it is known that some tumors use checkpoint systems to evade antitumor immune response. The treatment of advanced NSCLC by immunotherapy, such as immune-checkpoint blockade targeting the programmed cell death protein-1 (PD1/PDL1), has led to significant clinical benefit either as monotherapy or in combination therapy [4].

1.3 Need for Tumor Response Assessment

The landscape of novel cancer therapies is undergoing fundamental changes, with great promise in the immunotherapy trials as illustrated by the United States Food and Drug Administration (FDA) approval of multiple checkpoint inhibitors for various cancer indications, a monoclonal antibody (mAb), ipilimumab, for treatment of metastatic melanoma [12] and a vaccine for prostate cancers as the first vaccine against non-viral cancers [13]. There is a pressing need for accurate, timely assessment of immunotherapy treatment response in cancer patients to improve clinical management and facilitate drug development. A standard for response assessment is measuring tumor size with CT or MR and then classifying tumor size reduction according to RECIST [8]. RECIST and other standard response measures are ill suited to monitor response to immunotherapy, largely due to “pseudoprogression” caused by immune mediated increase in contrast enhancement. However, molecular imaging can measure important biologic responses that precede tumor size reduction, such as cellular metabolism, proliferation, and vascularity.

1.4 A Specific T-Cell Activation Imaging Agent for Tumor Response Assessment

Early preclinical and clinical studies have shown promise for immunotherapy treatments for several malignancies [22]. Immunotherapy is expected to grow in importance; however, it presents

difficult challenges for response assessment. For instance, successfully treated tumors may actually increase in size after therapy due to inflammation and only later shrink [25]. RECIST criteria [8] designed to detect early effects of cytotoxic agents by size reduction, or the more recently proposed immune-related response criteria (irRC) [19] do not allow an early assessment of immunotherapeutic response since both depend on tumor size change. Furthermore, FDG PET is confounded by inflammatory effects causing hypermetabolism [2, 11]. Thus, it is imperative to develop new imaging and analysis protocols to evaluate immune-checkpoint blockade approaches. A method that evaluates T cell activation would permit an assessment of a basic first step in the process of assessing immunotherapy efficacy.

1.5 Investigational Agent: [¹⁸F]F-AraG

CellSight Technologies (CST), Inc. is a company that is developing a suite of PET tracers targeted at visualizing immune response early in a patient's immunotherapy regimen. Their lead PET imaging tracer targeted at imaging activated T-cells is a fluorine-18-labeled analog of an FDA-approved drug Nelarabine [¹⁸F]F-AraG, trade name VisAcT. VisAcT is independent of the type of immunotherapy regimen being administered - adoptive cell therapy, checkpoint inhibitors, cancer vaccines or a combination of immunotherapy and conventional medicines. VisAcT is relatively specific to activated T-cells that are critical to any immune modulated therapy. In vivo, real time imaging of activated T-cells in solid tumors before and at a timepoint during and after checkpoint inhibitor therapy (CkIT therapy) can help understand the effects of check point blockade therapy. Additionally, in vivo whole-body imaging of activated T-cells can provide critical information about the effect of immunomodulation in autoimmune diseases, as well as help their prediction as adverse events.

1.5.1 Preclinical Characterization

Molecular imaging of immune activation by positron emission tomography (PET) is a potential noninvasive strategy to monitor immune activation after treatment with immunotherapy. Increased activity of nucleoside salvage pathways has been associated with the proliferation of adaptive and innate immune cells [10, 24]. In preclinical models of cancer and autoimmunity, the PET probe [¹⁸F]-2-fluoro-d-(arabino-furanosyl)cytosine ([¹⁸F]-FAC), which targets the deoxycytidine salvage pathway, was shown to localize to sites of immune activation [21] and is predominantly accumulated in proliferative CD8+ T-cells [17].

Recently, a radiofluorinated AraG imaging agent, [¹⁸F]F-AraG(2'-deoxy-2'-fluoro-9-β-D-arabino-furanosylguanine; trade name VisAcT) was synthesized [18] with a goal of development for human use. F-AraG is a fluorinated purine derivative with selective T-cell toxicity. A water-soluble AraG prodrug, Nelarabine, is FDA approved for the treatment of relapsed T-cell acute lymphoblastic leukemia and T-cell lymphoblastic lymphomas [7]. [¹⁸F]F-AraG preferentially accumulates in murine and human activated T-cells than in naive T-cells (Figure 1).

[¹⁸F]F-AraG was evaluated in three different preclinical models: rheumatoid arthritis [9], GvHD [23], colon cancer [14].

Figure 1: [¹⁸F]F AraG accumulation in activated T cells.

[figure not shown]

Figure 1: [¹⁸F]F-AraG preferentially accumulates in activated T-cells than in naive T-cells. **A)** Uptake of [¹⁸F]F-AraG in human and mouse primary T-cells post-stimulation. **B)** Pan T-cells were isolated from spleen and lymph nodes of mice. Untreated cells as well as CD3/CD28 activated T-cells (48 hours) were incubated with [¹⁸F]F-AraG before subcutaneous implantation into the shoulders before PET/CT imaging.

The accumulation of [¹⁸F]F-AraG in human activated T-cells is also significantly higher than other immune cells, including B cells, macrophages, and dendritic cells [14]. Furthermore, endogenously induced anti-tumor immune response in a viral induced rhabdomyosarcoma (MSV) mouse model was correlated with enhanced [¹⁸F]F-AraG uptake within the tumors (Figure 2A). Analysis of isolated tumors showed that tracer preferentially accumulated in activated CD8⁺ T-cells (Figure 2B).

[figure not shown]
Figure 2: Visualization of endogenously induced anti-tumor immune response

Figure 2: Visualization of endogenously induced anti-tumor immune response in a viral induced rhabdomyosarcoma (MSV) mouse model with [¹⁸F]F-AraG PET. **A)** Viral induced rhabdomyosarcoma was implanted in the left hindleg, and P815 mastocytoma (control) was implanted in the right shoulder. PET/CT was performed on Day 14 during the peak anti-tumor immune response in the rhabdomyosarcoma model. **B)** CD8⁺, CD4⁺ and C19⁺ cells were isolated from rhabdomyosarcoma tumor one hour after probe injection for radioactivity assay. Lymphocytes take up more than 80% of tumor associated [¹⁸F]F-AraG, with CD8⁺ and CD4⁺ cells acquiring the largest portion of the tracer (72%). The low uptake in B cells (CD19) is only observed in mice. Human B cells do not accumulate the tracer. **C)** FACS analyses of the isolated lymphocytes showed an activated phenotype (CD44⁺ CD62L⁻) in majority of CD8⁺ (79.9±11.5) and CD4⁺ cells (88.3±11.7). Error bars represent standard deviation.

1.5.2 Clinical experience

The first-in-human study of [¹⁸F]F-AraG was performed at UCSF in 2015 (abstract of meeting presentation available here:

<http://www.wmis.org/meetings/archives-of-past-meetings/wmic-2015-first-in-human-study-3/>.

[¹⁸F]F-AraG was administered at a subpharmacologic, tracer microdose consistent with imaging practices in six healthy volunteers (3 males and 3 females). The distribution of the tracer was evaluated over the first 4 hours after injection. A representative whole body PET/MR image in a healthy volunteer is shown in Figure 3 ([23]; [¹⁸F]F-AraG Investigator's Brochure). The tracer was well tolerated by all patients and there were no > Grade 1 adverse events (AE). The only AE that occurred in more than 1 volunteer was positive white blood cell (WBC) esterase in the urinalysis without urinary symptoms. Normal uptake was seen in the clearance organs: liver, kidneys and bladder. There appeared to be uptake in the thyroid and parotid glands, as well as

limited accumulation in the cardiac muscle. In these first-in human studies, no additional drugs were administered to subjects as the biodistribution was determined for radiation dose estimates. [23].

Figure 3: Whole body [¹⁸F]F AraG PET image in a healthy volunteer.

[figure not shown]

Figure 3: Maximum intensity projection (MIP) of a whole body [¹⁸F]F-AraG PET image of a healthy volunteer acquired 90 minutes post infusion.

[¹⁸F]F-AraG is currently being tested in several Phase I/II clinical trials. The clinical trials aim to evaluate the use of [¹⁸F]F-AraG in cancer patients undergoing immunotherapy. Cancer types include solid tumors of all types including, among others, lung cancer, melanoma, breast cancer and head & neck cancer. Non-oncology focused trials include an HIV trial at UCSF to help see differences in repositories of T cells in HIV patients and a trial at Stanford is determining if [¹⁸F]F-AraG will be useful as an early predictor of Graft vs Host Disease.

Investigators from Stanford have reported early clinical evidence that [¹⁸F]F-AraG PET scans demonstrate imaging of activated T-cells *in vivo*. In a study that aims to evaluate immunological response to Anti-PD-1 treatment in squamous cell carcinoma of the head and neck (SCCHN),

investigators reported a correlation in the change in total SUV and change in the CD8+T-cells post PD-1 antibody infusion (Figure 4).

Figure 4: [¹⁸F]F-AraG PET/CT images pre and post Anti PD 1 Ab therapy.

[figure not shown]

2. STUDY RATIONALE

Given that immunotherapeutic strategies, in particular immune checkpoint antibodies, focus on the generation of T-cell-based antitumor immunity, uptake of [¹⁸F]F-AraG within the tumor is hypothesized to correlate with T-cell mediated immune response seen in the biopsy samples of cancer patients treated with immune checkpoint blockade. Correlation of pre- and post-treatment intratumoral immune infiltration by means of PET imaging will guide the development of future

clinical trials investigating the role of [¹⁸F]F-AraG in the monitoring of anti-tumor immune responses. Therefore, proper quantification of [¹⁸F]F-AraG uptake in tumor lesions, and understanding its relation with physiologic uptake in background tissues is important. *Note: checkpoint therapy in this study is standard-of-care and is not under investigation.*

The distribution of radiotracer activity depends on post-injection imaging time for both anatomical structures and pathologic processes. Anatomic structures with physiologic uptake and pathologic abnormalities are likely to be characterized by distinct time-activity curves [3]. Therefore, the pharmacokinetic relationship between tumor activity and a variety of tissue background activity is important, which is best understood from dynamic images. Dynamic imaging of cancer subjects pre- and post-treatment is expected to provide data to establish this relationship between tumor and background, as well as the effect of treatment on the relationship.

While understanding tumor vs background activity in cancer patients is important, such subjects are likely to have prior or ongoing treatment, which may affect accurate baselining. Therefore, understanding normal tissue activity in healthy volunteers in whom radiotracer distribution is likely unencumbered by any effect of prior or ongoing treatment can be important to establish baseline dynamic data. In addition, healthy volunteers are likely to tolerate the long dynamic scan better than cancer subjects, improving the chances of obtaining standard baseline data.

Available PET/CT scanners can obtain dynamic images only on a portion of the body as large as their axial field of view, generally anywhere between 15-30 cm. The 194 cm long uEXPLORER total-body PET scanner is the world's first device to offer the ability to tomographically image all parts of the body simultaneously. Thus, the uEXPLORER PET/CT (now commercially available and with FDA 510(k) clearance) is the only scanner in the world capable of acquiring total-body dynamic images.

In this pilot study, 2-4 healthy volunteers will undergo [¹⁸F]F-AraG dynamic imaging on the uEXPLORER total body PET/CT scanner to obtain preliminary data regarding pharmacokinetics and early biodistribution images. In addition, 2-4 patients with NSCLC and planned for standard-of-care PD-1/PD-L1 immunotherapy will undergo [¹⁸F]F-AraG dynamic imaging similarly on the uEXPLORER total body PET/CT scanner to obtain data regarding pharmacokinetics of the tracer in tumor lesions in the context of normal tissue uptake. An optional second similar scan will be performed 7-14 days after the first dose of immunotherapy to explore and document any treatment related changes in [¹⁸F]F-AraG uptake and kinetics.

The study and data collected will be important to recommend an ideal time to acquire a whole body static scan using conventional and widely available PET/CT scanners for adequate tumor to background contrast and quantification, which in turn, will be essential for further clinical development of [¹⁸F]F-AraG to aid the monitoring of anti-tumor immune responses.

3. OBJECTIVES

The study is exploratory in nature with the following objectives:

3.1 Primary Objectives

- To obtain preliminary data on the baseline whole-body pharmacokinetics of [¹⁸F]F-AraG physiologic uptake in various healthy tissues using the uEXPLORER PET/CT scanner.
- To obtain preliminary data on the pharmacokinetics of [¹⁸F]F-AraG pathologic uptake in tumor lesions relative to uptake in background tissues in NSCLC subjects using the uEXPLORER PET/CT scanner.
- To recommend an ideal time window post [¹⁸F]F-AraG infusion to acquire static whole-body scans using standard PET scanners used in clinical care.

3.2 Secondary Objectives

- To assess [¹⁸F]-AraG uptake in NSCLC before and after the first dose of PD-1/PD-L1 immunotherapy.

4. STUDY POPULATION

4.1 Inclusion Criteria

Subjects are eligible if they meet ALL of the following criteria:

For all subjects:

1. Age \geq 18 years.
2. Ability to understand the purposes and risks of the trial and has signed an IRB-approved informed consent form.
3. Willingness and ability to comply with all protocol required procedures.
4. For men and women of child-producing potential, willingness to use of effective double barrier contraceptive methods during the study, up to 1 day after the last administration of the investigational product.

For NSCLC subjects only:

5. Patients with histologically confirmed advanced, locally advanced, or localized NSCLC.
6. Planned to undergo treatment with a PD-1 or PD-L1 inhibitor either as 1) monotherapy or as combination therapy with concurrent chemotherapy as treatment for advanced/metastatic disease 2) As consolidation therapy following chemoradiation for locally advanced disease or 3) As induction therapy either as monotherapy or combination therapy with chemotherapy prior to planned surgical resection

7. At least 1 tumor lesion > 1 cm (cannot be only in liver) documented on CT or MRI or FDG-PET/CT (RECIST criteria 1.1; >1.5 cm for nodal lesions) within 45 days prior to scan date.
8. Per investigator's assessment and in consultation with oncologists, at least one eligible lesion must be sufficiently separated from tissues with known high [¹⁸F]F-AraG uptake, such as salivary glands, bladder, liver and kidneys so that quantification will be feasible.
9. Eastern Cooperative Oncology Group (ECOG) performance status ≤ 2
10. Meeting all clinical safety lab values per institution's standard of care, or Investigator's discretion, for patients receiving cancer treatment.

4.2 Exclusion Criteria

Subjects are not eligible if they meet ANY of the following criteria:

1. Serious comorbidities (nonmalignant disease or other conditions) that in the opinion of the investigator could compromise protocol objectives.
2. History of recent COVID-19 infection within the last 2 months OR history of COVID requiring hospitalization with lung injury at Investigator's discretion
3. Subjects with a diagnosis of immunodeficiency or receiving systemic steroid therapy or any other form of immunosuppressive therapy within 7 days prior to the scan
4. Subjects receiving therapy with nucleoside analogs including but not limited to: acyclovir, valacyclovir, penciclovir, famciclovir, ganciclovir, ribavirin, valganciclovir, ganciclovir
5. Pregnant women or nursing mothers
6. Body weight more than 240 kg (529 pounds)

For NSCLC subjects only:

7. Prior Treatment with anti-PD-1/PD-L1 immunotherapy.

For Healthy subjects

8. No primary care physician

5. STUDY DESIGN

Protocol CST-FARAG-203 is a pilot study using the uEXPLORER total-body PET/CT system to acquire dynamic [¹⁸F]F-AraG scan data in healthy individuals and patients with NSCLC.

Screening will consist of eligibility confirmation, the patient signing the consent form, and any assessments outlined in the study calendars below. This will also include a query about status and date of COVID-19 vaccination.

Eligible healthy subjects will undergo a single dynamic [¹⁸F]F-AraG PET/CT scan (of duration up to 90-minutes) on the uEXPLORER PET/CT scanner within 28 days of screening or on the day of screening if possible and convenient to the subject. There will be a follow-up visit or call 7 days after the scan to assess any AEs that could be attributed to either the scan or the administration of [¹⁸F]F-AraG.

Eligible subjects with NSCLC who are planned to receive PD-1/PD-L1 immunotherapy will undergo a pre-therapy dynamic [¹⁸F]F-AraG PET/CT scan, and an optional post-therapy (first dose only) dynamic [¹⁸F]F-AraG PET/CT scan on the uEXPLORER total-body scanner.

For each enrolled patient, [¹⁸F]F-AraG will be administered by a licensed Nuclear Medicine technologist under the supervision of a board-certified Nuclear Medicine physician (ABNM or ABR certified) on an outpatient basis. It will be administered as a single bolus injection of 5 mCi +/-20% IV into a vein. Vital signs will be assessed just prior to and after completion of dynamic [¹⁸F]F-AraG PET scan.

For each scan, the subject will be prepared according to the site's standard procedures and asked to void the bladder immediately prior to imaging. For the scan, an intravenous (IV) line will be placed in a vein and the subject will be positioned supine on the scanner table. The PET/CT imaging will begin with a low-dose CT scan on the uEXPLORER PET/CT scanner. This CT scan will provide information for anatomic localization and attenuation correction purposes.

[¹⁸F]F-AraG will then be infused as above and a 90-minute dynamic PET scan will be performed on the uEXPLORER. The IV line will be removed after dynamic acquisition. For subjects who may not be able to undergo a 90-minute dynamic scan, a 60-minute dynamic PET scan will be performed, followed by a 10-minute static scan starting at 80 minutes post [¹⁸F]F-AraG infusion. The separate static scan at 80 minutes will be obtained along with an ultra-low-dose CT which is needed for attenuation correction of this separate scan.

The study will be an open label, non-randomized, single arm trial. Patients and care providers will not be blinded to any part of the study.

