7.1.2 Radiation Risk

Each patient will receive up to two 5 mCi +/-20% doses of [¹⁸F]F-AraG. Dosimetry assessment estimated an effective dose of 0.58 and 0.62 mSv/mCi for males and females, respectively. Risks from the PET/CT itself include additional radiation exposure from the CT attenuation correction scan (estimated to be 10 mSv for each low dose CT scan and 1 mSv for each ultra low dose CT scan). The table below shows the estimated effective radiation dose received by the subjects in this protocol:

	Healthy Subjects	NSCLC Patients	NSCLC Patients who cannot undergo 90 minutes continuous scanning
Low dose CT scan	10 mSv	10 mSv	10 mSv
Ultra low dose CT scan	N/A	N/A	1 mSv
[¹⁸F]-AraG PET scan	2.9 +/- 0.29 mSv(male) 3.1 +/- 0.31 mSv(female)	2.9 +/- 0.29 mSv(male) 3.1 +/- 0.31 mSv(female)	2.9 +/- 0.29 mSv(male) 3.1 +/- 0.31 mSv(female)
Total estimated dose	12.9 +/- 0.29 mSv(male) 13.1 +/- 0.31 mSv(female)	12.9 +/- 0.29 mSv(male) 13.1 +/- 0.31 mSv(female)	13.9 +/- 0.29 mSv(male) 14.1 +/- 0.31 mSv(female)
Number of scans	1	2	2
Maximum estimated dose	13.2 mSv (male) 13.4 mSv (female)	26.4 mSv (male) 26.8 mSv (female)	27.4 mSv (male) 27.8 mSv (female)

The total estimated dose from the combined PET/CT examination will be 13.4 mSv or less for normal subjects and 27.8 mSv or less for patients with NSCLC. The use of radiation involves minimal risk and is required to obtain the desired research information.

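### The maximum radiation doses in Section 7.1.2 are too low: they reproduce only with a 10% spread where 20% in activity is permitted, and the NSCLC fallback total counts one extra CT over two scans

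*Combined protocol and SAP*

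**What the plan says.** Section 5 sets the administered activity as "a single bolus injection of 5 mCi +/-20% IV into a vein". Section 7.1.2 repeats the tolerance above its dose table: "Each patient will receive up to two 5 mCi +/-20% doses". The same section gives the effective dose as 0.58 mSv/mCi for males and 0.62 mSv/mCi for females, each low-dose CT as 10 mSv and each ultra-low-dose CT as 1 mSv.

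The table's PET row reads "2.9 +/- 0.29 mSv(male) 3.1 +/- 0.31 mSv(female") in all three columns, without saying what the spread represents. Its maximum row gives, male/female:

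- healthy subjects, one scan: 13.2/13.4 mSv
- NSCLC patients, two scans: 26.4/26.8 mSv
- the column headed "NSCLC Patients who cannot undergo 90 minutes continuous scanning", two scans: 27.4/27.8 mSv

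The sentence under the table turns the higher values into ceilings of 13.4 mSv for normal subjects and 27.8 mSv for NSCLC patients.

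On the shortened procedure, Section 5 says: "For subjects who may not be able to undergo a 90-minute dynamic scan, a 60-minute dynamic PET scan will be performed". It continues: "The separate static scan at 80 minutes will be obtained along with an ultra-low-dose CT". It names no cohort. The table marks the ultra-low-dose CT as not applicable to healthy subjects.

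**The concern.** A stated maximum should be a figure that the permitted procedures cannot exceed. Here a dose inside the allowed activity range exceeds it, with no deviation and no unusual event. Healthy volunteers are the sensitive group, because Section 8 says that subjects get no direct benefit and the ceiling is what the protocol tells its reviewers about their exposure.

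The NSCLC fallback column has a further problem of its own: its total does not follow from its own per-scan figure and its own number of scans.

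What is at stake is the accuracy of a safety statement. No endpoint, analysis population or stopping rule uses these numbers.

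**Working it through.** **Inputs.** Activity 5 mCi, tolerance 20%, so at most 5 × 1.20 = 6 mCi (Sections 5 and 7.1.2). Coefficients 0.58/0.62 mSv/mCi, CT doses of 10 and 1 mSv, and the numbers of scans (all Section 7.1.2). Pairs are male/female.

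**Formula.** Dose per scan = 10 + (5 × coefficient) × (1 + spread) + 1 if the fallback is used. Maximum = dose per scan × number of scans.

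**The plan's own figures.** PET dose: 5 × 0.58 = 2.9 and 5 × 0.62 = 3.1 mSv. The table's spread is 0.29/2.9 = 0.31/3.1 = 10%.

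- Healthy: 10 + 2.9 + 0.29 = 13.19; 10 + 3.1 + 0.31 = 13.41. These match 13.2/13.4.
- NSCLC, two 90-minute scans: 2 × 13.19 = 26.38; 2 × 13.41 = 26.82. These match 26.4/26.8.
- NSCLC fallback: 2 × 13.19 + 1 = 27.38; 2 × 13.41 + 1 = 27.82. These match 27.4/27.8, but only with one ultra-low-dose CT. The column shows 13.9/14.1 mSv per scan, which already includes that CT, and two scans: 2 × (13.9 + 0.29) = 28.38; 2 × (14.1 + 0.31) = 28.82.

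**At the permitted 6 mCi.** PET dose: 6 × 0.58 = 3.48; 6 × 0.62 = 3.72 mSv.

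| Case | Stated | At 6 mCi | Shortfall |
|---|---|---|---|
| Healthy, one 90-minute scan | 13.2/13.4 | 13.48/13.72 | 0.28/0.32 (2.1%/2.4%) |
| NSCLC, two 90-minute scans | 26.4/26.8 | 26.96/27.44 | 0.56/0.64 (2.1%/2.4%) |
| NSCLC, fallback at both scans | 27.4/27.8 | 28.96/29.44 | 1.56/1.64 (5.7%/5.9%) |

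In the last row, 1 mSv of the shortfall is the uncounted CT and the rest is activity. If a patient uses the fallback at only one of two scans, the totals are 26.96 + 1 = 27.96 and 27.44 + 1 = 28.44, still above the stated values.

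**Where the healthy ceiling is crossed.** (13.2 − 10)/0.58 = 5.52 mCi; (13.4 − 10)/0.62 = 5.48 mCi. Both lie inside the permitted range.

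**If a volunteer were given the fallback.** 13.48 + 1 = 14.48; 13.72 + 1 = 14.72 mSv.

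**The case against.** **The 10% may not be an activity tolerance.** The table does not label its spread, which could be uncertainty in the dosimetry. That stands: reading it as a mistaken activity tolerance is an inference. It does not rescue the maxima. If the 10% is dosimetric, the table leaves the activity tolerance out altogether, and 6 mCi at the stated coefficients still gives 13.48/13.72 mSv.

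**The tolerance may not apply to volunteers.** Section 5 introduces the injection with "For each enrolled patient", which could be read as NSCLC only. Section 5 gives no other activity for volunteers, and the table assigns them the same PET dose, so that reading would leave them without a specified dose.

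**The fallback column may mean one shortened scan out of two.** That would explain a single 1 mSv. But the column carries the extra CT in its per-scan total and lists two scans, and Section 5 does not limit the fallback to one visit.

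**A reader might infer that the healthy maximum is 1 mSv low because volunteers can have the fallback.** The documents do not support stating this as an established error. The table's not-applicable entry and its NSCLC-only heading are specific, and Section 2 expects volunteers to tolerate the long scan better. Section 5 is generic, and its cohort nouns are loose. On the other side, no sentence in Section 5 excludes volunteers, the scan procedure there is shared by both cohorts, and their scan is described as "of duration up to 90-minutes". What remains is a wording mismatch in which either section may be the one to change.

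**Materiality.** The 10 mSv CT figure is itself a round estimate that makes up most of the total, and the unconditional shortfall for a volunteer is about 0.3 mSv. This is correct and is why the point is minor.

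**Conclusion.** The point holds as a minor error in a stated safety figure. On the protocol's own coefficients and CT doses, the maxima at permitted activity are 13.5/13.7 mSv for healthy subjects, 27.0/27.4 mSv for NSCLC patients with two 90-minute scans, and 29.0/29.4 mSv for NSCLC patients who use the fallback twice. The healthy and 90-minute NSCLC results need only the 20% tolerance and do not depend on how the fallback is read. The 29.0/29.4 figure assumes that the optional second scan is done, that the fallback is used both times and that both doses are 6 mCi, which is the right basis for a maximum.

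The mismatch over who may use the fallback is secondary. It adds 1 mSv for a volunteer only if the site applies the fallback despite the table.

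At most 4 healthy and 4 NSCLC subjects are concerned. A reader might go further and infer that the primary results are affected. They are not: the dose table feeds no analysis, and under Section 11.4.1 a volunteer who stops early still belongs to the efficacy population.

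**What to change.** 1. Recompute the maximum row in Section 7.1.2 at 6 mCi, with one ultra-low-dose CT for every fallback scan: 13.5/13.7, 27.0/27.4 and 29.0/29.4 mSv.
2. Say what the spread of 0.29/0.31 represents. If it is activity tolerance, change it to 0.58/0.62 mSv and update the per-scan totals. If it is dosimetric uncertainty, keep it, label it, and state the activity tolerance separately.
3. Correct the sentence below the table: 13.4 becomes 13.7 mSv for normal subjects (14.7 if volunteers may use the fallback), and 27.8 becomes 29.4 mSv for NSCLC patients. Correct any matching figure in the consent form.
4. Settle the scope of the fallback. Either limit the Section 5 sentence to NSCLC subjects, or add a healthy fallback column with a maximum of 14.5/14.7 mSv.

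The cost is one table, one sentence and one scope decision. Section 15.4 treats the consent form as part of the protocol, and Sections 13.3 and 15.3 route such changes through the IRB, so the edits belong in one amendment. Limiting the fallback to NSCLC subjects has a small scientific price: a volunteer who cannot finish gives no static data at 80 to 90 minutes, and Section 10.3 looks at activity up to 90 minutes when choosing the recommended window.
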